5.2. Patient Exclusion Criteria

Patients are excluded from the study if any of the following criteria apply:

- 1. Clinically significant or severely symptomatic intercurrent infection
- 2. Pregnant or lactating
- 3. Any other issue which, in the opinion of the treating physician, would make the patient ineligible for the study
- 4. For Group 1, anti-neoplastic therapy after HSCT and prior to or during dosing of MT-401
- 5. For Group 2, concomitant anti-neoplastic therapy during or after dosing of MT-401

Confidential Page 35 of 74

- 6. Evidence of acute or chronic GVHD ≥Grade 2 (exception: acute or chronic Grade 2 GVHD of skin allowed if stable) within one week prior to receiving MT-401
- 7. Taking systemic corticosteroids (exception: physiological doses of steroids allowed)
- 8. On other investigational therapy post-HSCT
- 9. Anti-thymocyte globulin or Campath within 28 days of MT-401 infusion

5.3. Donor Inclusion Criteria

Donors for allogeneic stem cell transplants must be considered suitable for and consent to stem cell donation, as per the standard operating procedures of the stem cell transplant program. If a donor has been chosen for the transplant, that same donor will also be used for to manufacture the T cell product provided that there are no new reasons for ineligibility since the stem cell collection. The donors will be evaluated as per standard institutional guidelines. The donor clearance by the National Marrow Donor Program (NMDP) is also acceptable.

Leukapheresis material will be collected from the same HSCT donor to manufacture MT-401 for the patient.

5.4. Lifestyle Considerations

No restrictions for diet; caffeine, alcohol, and tobacco; or activity are required during this study.

5.5. Screen Failures

Screen failures are defined as patients who consent to participate in the clinical study but are not subsequently randomly assigned to MT-401 (Groups 1) or fail to receive at least one dose of MT-401 (Group 2). Minimal data will be collected for screen failures, which will include demography, screen failure details, eligibility criteria, and any SAE.

Individuals who do not meet the criteria for participation in this study (screen failure) may be rescreened. Rescreened patients should be assigned the same patient number as for the initial screening. Repeating laboratory tests that did not meet eligibility criteria during the 28-day screening period does not constitute rescreening. If a repeated laboratory value meets eligibility criteria, that test must be repeated again to confirm eligibility.

Patients may be rescreened up to 2 times after the initial screening. The interval between rescreenings should be at least 1 week. Any laboratory tests and procedures falling outside original 28-day period need to be repeated. Local laboratories will be used to assess eligibility.

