Study treatment is administered for all patients (except SoC - Group 1- Arm B) on Day 0 and every 2 weeks for a planned maximum of 3 doses. Patients randomized to SoC (Group 1B) at 80 days post-transplant may crossover to the relapse group (Group 2) if the patient is found to have relapse of disease (MRD* or frank relapse) and the subgroup is open and/or Sponsor agreement. After relapse and prior to bridging chemotherapy, the patient should perform assessments associated with the Screening visit if not already completed. The patient should perform the assessments associated with Baseline following bridging chemotherapy and prior to MT-401 administration. The patient will have their visits reset and have their MT-401 administered on Day 0 and follow the schedule of events from that point forward. Group 1- Arm B (SoC) patients will continue to follow the SoA minus administration of MT-401. Refer to Section 6 for additional dosing details. Administration of MT-401 can be delayed due to management of AEs or other toxicities, but patients should resume T cell infusions within 2 weeks of their scheduled dose. If greater than 2 weeks is needed, Sponsor will determine if patient can resume T cells infusions.

m All AEs and SAEs, from Day 0 and Baseline, respectively, to the Week 12 Visit will be collected; after Week 12, only treatment-related AEs and SAEs will be collected.

ⁿ Detailed studies outlined in Section 8.8.

o Additional details regarding the PRO questionnaire and associated instructions will be provided in a separate document.

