4.4. Study Period and End of Study Definitions

Screening: begins when the informed consent form (ICF) is first signed. The patient is enrolled once Screening tests have been completed successfully and prior to HSCT for Group 1 patients, and prior to the start of manufacturing for Group 2 patients.

Baseline: A re-assessment of eligibility will occur within 14 days prior to group assignment for Group 1 to confirm eligibility has been met.

Randomization: Randomization to MT-401 or SoC for patients in Group 1 will occur once eligibility has been reconfirmed post-HSCT and groups have been assigned.

Study Period: begins the day of the first patient's first dose of MT-401 and ends at End of Study.

Confidential Page 32 of 74

- Study Treatment Period: begins with the day of the patient's first study treatment and ends the day the patient and investigator agree that the patient will discontinue study treatment or after all doses of MT-401 have been administered (whichever is earlier) (including for the Safety Lead-in portion of the study).
- Follow-up Period: begins the day after the study treatment period ends and is complete the day of the patient's death, withdrawal of consent, loss-to-follow-up or End of Study (whichever is earlier). It includes safety follow-up visits and additional long-term follow-up visits, as outlined in the SoA (Table 1):
 - Active Follow-up: occurs after the last dose of MT-401 has been administered until
 patient relapses/progresses or declines any additional study visits (but patient may
 continue with survival follow-up).
 - Survival Follow-up: begins the day a patient relapses as determined by investigator or declines any additional study visits and ends with the End of Study.

End of Study: A patient is considered to have completed the study if he/she has completed the planned study treatment and follow-up periods of the study as per SoA, withdrawn, patient's death or lost to follow-up.

No intervention following the End of Study is planned, and patients will return to their physician for further management.

4.5. 3+3 Design (Safety Lead-in and Cohorts III-V)

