 - Blood: Hemoglobin \geq 7.0 g/dL (can be transfused)
 - Liver: Bilirubin ≤1.5X upper limit of normal; aspartate aminotransferase ≤3X upper limit of normal
 - Renal: Serum creatinine ≤2X upper limit of normal or measured or calculated creatinine clearance >45mL/min
- 7. Sexually active patients must be willing to utilize one of the highly effective birth control methods or practice complete abstinence starting from Screening for T cell infusion until 6 months after the last T cell infusion (see details in Section 8.3.5). Male patients who are sexually active must agree to use a condom during this period.
- 8. Patients are allowed to be on experimental conditioning regimens prior to transplant if no planned maintenance therapy post-transplant.
- 9. In Group 2, patients may receive bridging therapy at the investigators' discretion in situations where MT-401 is not ready for administration or the treating physician believes the patient would benefit (particularly in cases of high tumor burden) for ≤6 months as long as the following criteria are met:
 - Disease assessment including bone marrow biopsy to be performed within 14 days prior to administration of MT-401 (patients may receive MT-401 even if CR MRD is achieved post-bridging therapy but will be analyzed separately; additionally, patients must have ≤30% bone marrow blasts)
 - At least 4 half-lives or 1 week has passed after administration of bridging therapy whichever is shorter

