9.2. Populations for Analyses

Populations for analyses are defined in Table 8.

Table 8. Populations for Analysis

Population	Description
All enrolled patients	All patients who sign the ICF and donor undergoes leukapheresis
All randomized patients in Phase 2 (Adjuvant - Group 1 only)	All patients in Group 1 who are randomized with final dose and manufacturing process, and are MRD prior to randomization by central testing and local testing (if a local test was a lso performed). Efficacy analyses for Group 1 will be conducted in this population. A patient randomized based on negative MRD result per central test but confirmed to be MRD will be excluded from Group 1 analyses. The patient will
All treated patients	be included in Group 2 Subgroup D analyses if treated with MT-401. All patients who receive at least one dose of MT-401 or were randomized to SoC. Patients whose product includes fewer cells or does not meet specifications may still be treated, but will be summarized separately from patients whose product meets specifications. For - Group 1, safety analyses will be conducted in this population, and safety data for patients randomized to SoC will also be shown for reference. For - Group 2, all efficacy analyses and safety analyses will be conducted in this population. For the Safety Lead-in (Cohorts I and II) and Cohorts III-V, all efficacy and safety analyses will be conducted in this population.
DLT-eva luable	All patients in the Safety Lead-in (Cohorts I and II) and Cohorts III-V who receive at least one dose of MT-401 and have had the opportunity to be followed for 28 days from the initial MT-401 infusion or have experienced a DLT.
Per-protocol in Phase 2	All treated patients, as defined above, who have no major protocol deviations. Select efficacy analyses for Group 1 and Group 2 will be conducted in this population for sensitivity analysis.

Confidential Page 51 of 74

Abbreviations: DLT=dose-limiting toxicity; ICF=informed consent form; MRD=minimal residual disease; SoC=standard of care

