complete response is defined as the time between the date of first documented response of CR_{MRD} - to the date of the first documented relapse per ELN recommendations or death due to any cause, whichever occurs first.

The CR rate from Group 2 Subgroup C will be evaluated in the context of results from an ongoing retrospective study of AML patients who are similar to the inclusion/exclusion criteria of Group 2 Subgroup C patients. Any comparison of Group 2 data to results from the retrospective study will be described in a separate SAP.

Censoring rules for DOCR are provided in Table 10.

Table 10: Censoring Scheme for Primary Definition of DOCR

Situation	Date of Event or Censoring	Outcome
Relapse per ELN recommendations	Date of first relapse	Event
Death without relapse	Date of death	Event
No relapse and no death	Date of last evaluable disease assessment	Censored
New anti-cancer therapy received without relapse reported prior to or on the same day as disease assessment	Date of last evaluable disease assessment on or prior to the date of initiation of subsequent therapy	Censored
Two or more consecutive missed scheduled disease assessments	Date of last evaluable disease assessment prior to the missed disease assessments	Censored

Abbreviations: AML=acute myeloid leukemia; RFS=relapse-free survival

Relapse includes either hematologic and/or molecular relapse as defined in Table 6 at any disease assessment.

The CR rate and the corresponding 95% exact CI will be calculated. The DOCR will be estimated using the KM product limit method. The KM estimate of the median DOCR and the DOCR rates at milestone timepoints will be reported along with the two-sided 95% CI.

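### The screen-failure definition in Protocol 5.5 wrongly takes in Arm B and merges enrolled-but-undosed Group 2 patients with screen failures, while the Group 2 CR rate is conditional on reaching infusion

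*Protocol*

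**What the plan says.** Protocol 5.5 makes a consented patient a screen failure if "not subsequently randomly assigned to MT-401 (Groups 1) or fail to receive at least one dose of MT-401 (Group 2". It adds: "Minimal data will be collected for screen failures, which will include demography, screen failure details, eligibility criteria, and any SAE".

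Other sections describe the same patients differently.

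- **Arm B.** The study-treatment footnote to Protocol Table 1 says: "Group 1- Arm B (SoC) patients will continue to follow the SoA minus administration of MT-401". Protocol Table 8 and SAP 7.2 count patients randomised to SoC in All Treated. SAP 7.4.1 analyses Group 1 efficacy in all randomised patients.
- **Group 2 enrolment.** Protocol 4.4 says "The patient is enrolled once Screening tests have been completed successfully" "and prior to the start of manufacturing for Group 2 patients" (two parts of one sentence; the part between them concerns Group 1). Protocol Table 8 defines All Enrolled as "All patients who sign the ICF and donor undergoes leukapheresis".
- **Group 2 analysis.** Protocol 9.3.3 defines the CR rate as a proportion of treated patients, and SAP 7.4.1 places Group 2 efficacy in All Treated.
- **External comparison.** Protocol 9.3.3 says: "The CR rate from Group 2 Subgroup C will be evaluated in the context of results from an ongoing retrospective study of AML patients". Any comparison is left to a separate SAP. SAP 6.1 and 7.4.4 mention a possible synthetic control on the same footing.

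**The concern.** Two things are wrong, and they differ in weight.

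The first is the Group 1 wording. Being assigned to SoC is a way of not being assigned to MT-401, so the definition covers the whole control arm. It also covers Group 1 patients who relapse before randomisation and move to Group 2. Sites use this section to decide what to record, so it should not contradict the schedule.

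The second is the substantive one. Between Group 2 enrolment and first infusion a patient may die, progress, lose eligibility or have no product. That loss is plausibly related to the course of the disease. Such patients are outside the CR denominator, and once labelled screen failures they have no disease or survival status on the list of data collected. A treated-only CR rate describes patients who survived and stayed eligible until infusion. That is a fair thing to estimate. It becomes a problem if the rate is set against an external cohort counted from relapse or from entry criteria.

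**Working it through.** **Step 1. Arm B.** About 75 of the 150 Group 1 patients are randomised to SoC (Protocol 9.1.1). Under 5.5 all of them meet the definition and would yield demography, screen-failure details, eligibility and SAEs only. Against this, Table 1 keeps them on the schedule and its footnote d plans a Week 0 visit for them. Table 8 and SAP 7.2 place them in the analysis sets, and SAP 7.1.5 defines treatment-emergent events for them. Only 5.5 excludes them, so 5.5 is the section in error.

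**Step 2. Path of an undosed Group 2 patient.**

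1. Enrolled after screening and before manufacturing (4.4).
2. May receive bridging therapy for up to 6 months, then needs a fresh disease assessment that meets the marrow-blast limit (5.1).
3. If never infused, becomes a screen failure (5.5).
4. The SAE item does not fill the gap: 8.3 gives death from disease progression as an example of something that is not an AE and so cannot be an SAE.
5. Not in the CR denominator (9.3.3; SAP 7.4.1). SAP 7.4.7.2 counts patients without a post-baseline assessment as non-responders, but within the treated set, so it does not bring these patients back.
6. Protocol 6.3 says all eligible enrolled Group 2 patients will be treated, which leaves no category for them.

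**Step 3. The plan's own figure.** Protocol Table 7 uses n = 30 per subgroup and a one-sided exact test at 0.05. For a historical rate of 20%, the smallest rejecting count is 11 of 30 (exact level 0.026). Power is 0.811 at 43% and 0.907 at 47%, and the exact 95% CI at 43% is 25-62%. The row reproduces. Its denominator is 30 treated patients.

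**Step 4. Effect of the denominator.** Let x be responders among 30 treated and f the share of enrolled patients never infused. The documents give no value for f; 10-30% is an assumption. Counting undosed patients as non-responders:

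number enrolled = 30/(1 - f); all-enrolled rate = (x/30)(1 - f); drop = (x/30) f.

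| Assumed f | Enrolled, rounded up | x = 9 (30% of treated): formula | x = 9: whole patients | x = 13 (43% of treated): formula | x = 13: whole patients |
|---|---|---|---|---|---|
| 10% | 34 | 27.0% | 9/34 = 26.5% | 39.0% | 13/34 = 38.2% |
| 20% | 38 | 24.0% | 9/38 = 23.7% | 34.7% | 13/38 = 34.2% |
| 30% | 43 | 21.0% | 9/43 = 20.9% | 30.3% | 13/43 = 30.2% |

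By the formula the drop is 3, 6 or 9 points from 30%, and 4, 9 or 13 points from 43%. Protocol 9.1.2 calls an increase in CR rate of more than 10-15% over historical rates clinically meaningful. The exact 95% CI for 9/30 is 15-49%.

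**The case against.** The other side has several good points.

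- **Arm B.** A reader might infer that control data would be lost. They would not: every operative section follows and analyses Arm B. This part is a drafting slip.
- **Cause.** A reader might infer that 5.5 removes undosed patients from the CR rate. It does not. The declared All Treated population does that, openly, and rewording 5.5 alone would leave the CR rate unchanged. All Treated is a legitimate primary set for a single-arm estimate whose sample size is not based on a formal power calculation.
- **Counts.** A reader might infer that the all-enrolled rate could never be recovered. SAP 7.3.1 already summarises disposition for all enrolled patients, with numbers in each analysis population, so an approximate rate could be worked out. What is missing is the disease and survival status of undosed patients and a pre-specified table.
- **Direction.** The retrospective cohort is to resemble Subgroup C on entry criteria, which include the pre-dose marrow requirement. It may already be restricted to patients who reached treatment. The separate SAP would settle this and is not among these documents.
- **Size.** The loss may be small: product with fewer cells or out of specification may still be given, six months is a ceiling on discretionary bridging, and the accelerated process takes about a week. The illustrated shift also lies within the confidence interval.

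All of this stands. The contradiction in 5.5, the missing data items and the absence of any rule matching the external cohort to the denominator remain. A shift that lies within the sampling interval is still systematic and adds to sampling error.

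**Conclusion.** The point holds in two parts. The Group 1 wording of 5.5 is an error that conflicts with the rest of the protocol and the SAP; it affects the classification of about 75 patients and does not threaten the RFS comparison. The Group 2 CR rate is conditional on reaching infusion, and the plan neither collects outcomes for enrolled patients who are not infused nor shows a rate that includes them.

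The stronger reading, that the treated-only rate is biased in favour of MT-401, is not supported as it stands. It needs an external cohort that is not restricted to patients who reached treatment, and the documents do not say whether it is. If it is not, the bias would favour MT-401 by an amount the documents do not allow one to state. The figure of 3-9 points on a 30% rate rests on an assumed 10-30% loss and on counting all undosed patients as non-responders.

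The rule does not reach every undosed patient either: an Arm A patient randomised but never infused is not a screen failure under 5.5, and the section does not mention Cohorts I-V.

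**What to change.** 1. **Protocol 5.5.** Define screen failures as consented patients who do not meet eligibility and are not randomised to MT-401 or SoC (Group 1) or not enrolled in Group 2.
2. **Enrolled, not treated.** Keep these patients as a separate category. Record the reason undosed, last disease status and survival status.
3. **SAP 7.2 and 7.4.4.** Keep All Treated as the primary CR population. Add a supportive CR rate in all patients enrolled into each Group 2 subgroup, with undosed patients as non-responders. Count from Group 2 entry, including Arm B crossover patients and those who relapse before randomisation. Their first consent and donor collection may precede Group 2 entry, so the Table 8 definition alone does not fix the starting point. Show patients who reach CR without MRD on bridging, and early-relapse patients, separately as Protocol 9.1.2 already does; otherwise the supportive rate would count failures on bridging and leave successes unaccounted for.
4. **Separate comparison SAP.** Align time zero and selection of the external cohort with whichever denominator is used.

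The cost is one reworded definition, a few eCRF fields and one supportive table per subgroup. No treatment rule changes. The downside is that a less favourable supportive figure will appear beside the primary CR rate.

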5.6. Dose-Limiting Toxicity Determination

A DLT is defined as one of the following AEs reported during the observation period (28 days from the day of the initial MT-401 infusion), if considered to be definitely, probably, or possibly related to MT-

Confidential Page 36 of 74

401 and deemed clinically significant by the investigator; and fulfills any of the following criterion using NCI CTCAE (Version 5.0) with the exceptions as noted below:

- 1. Grade 3-4 GVHD
- 2. Grade 3-4 toxicity felt to be related to, or resulting from CRS
 - Exception: Grade 3 and 4 expected reactions seen with the use of T cell-based immunotherapy, such as (but not limited to) fever and hypotension not requiring pressor support, will not be considered DLTs
- 3. Grade 3-4 infusion reactions that are persistent beyond 72 hours despite optimal medical management
- 4. Any other Grade 3-4 toxicity that is *not* pre-existing and/or *not* due to the underlying malignancy or infection or treatment of disease lasting for extended period of time despite optimal supportive care (for example, nausea, vomiting, and diarrhea lasting > 3 days; fatigue lasting > 7 days)
 - Exception: Laboratory abnormality deemed not to be clinically significant
- 5. Grade 5 toxicity (that is, death)

